### **8.3. Follow-up Phase**

Once a subject has completed the End-of-Treatment visit they will enter the Follow-up Phase. Subjects that withdraw from treatment for reasons other than progressive cGVHD or progression of their underlying malignancy will participate in ongoing response follow-up.

#### **8.3.1. Response Follow-up**

Subjects who discontinue ibrutinib/placebo for reasons other than progressive cGVHD or progression of underlying malignancy will be followed at pre-specified response assessment time points (Weeks 5, 13, 25 and every 12 weeks thereafter) by clinic visit until progressive disease or progression of underlying malignancy. During this period, the following procedures will be performed:

- Physical examination
- Vital signs
- Performance status (KPS/Lansky) ([Appendix C](#))
- Hematology
- Serum chemistry
- cGVHD activity assessment per NIH ([Appendix H](#) and [Appendix J](#))
- cGVHD response assessment ([Appendix I](#))
- Lee cGVHD Symptom Scale ([Appendix F](#))/SF-36 Questionnaire ([Appendix G](#))
- FEV1 every 12 weeks if prior FEV1 abnormal, every 24 weeks if prior FEV1 normal
- Review corticosteroid requirements and any new cGVHD treatment if applicable

#### **8.3.2. Long-Term Follow-up**

Once subjects have cGVHD progression, or have progression of their underlying malignancy (for subjects who have not withdrawn consent), they will be contacted approximately every 12 weeks ( $\pm 14$  days) by clinic visit or telephone to assess survival and the use of alternative cGVHD therapy. In addition, subjects who have progressive cGVHD will continue to have the Lee Symptom Scale and SF-36 assessments until the week 60 visit. Subjects will be contacted until death, subject withdrawal, lost to follow-up, or study termination by the Sponsor, whichever occurs first.

#### **8.3.3. Expected length of participation on study**

The Sponsor will continue to follow adult subjects up to approximately 3 years after the first subject was randomized. Adolescents (<22 years of age at the time of randomization) will be followed for up to 5 years after randomization; however, the study may close after the last patient below 18 years of age has exited the study if all other participating subjects have completed a minimum of 1 year of follow-up. Subjects may be rolled over to a long-term extension study for long-term follow-up.

## **9. SUBJECT COMPLETION AND WITHDRAWAL**

### **9.1. Completion**

A subject will be considered to have completed the study if he or she has died before the end of the study, has not been lost to follow up, or has not withdrawn consent before the end of study.

### **9.2. Discontinuation from Ibrutinib/Placebo**

Ibrutinib/placebo will be discontinued in the event of any of the following events:

- Subject begins treatment with another systemic therapy (including ECP) for cGVHD
- cGVHD progression
- Progression or relapse of the malignancy that was the indication for transplantation or development of PTLD
- Unacceptable toxicity: an intercurrent illness or AE that prevents further ibrutinib/placebo administration despite dose adjustment
- Noncompliance with study medication
- Investigator's decision (such as chronic noncompliance, significant protocol deviation, or best interest of the subject)
- Withdrawal of consent for treatment by subject
- Unblinding at primary efficacy analysis
- Study termination by Sponsor
- Subject becomes pregnant
- Death

All subjects, regardless of reason for discontinuation of ibrutinib/placebo will undergo an End-of-Treatment visit and be followed as outlined under [Section 8.3](#).

The investigator should notify the Sponsor within 24 hours if a subject discontinues ibrutinib/placebo treatment due to cGVHD progression and should provide documentation of cGVHD progression for review by the Sponsor's medical monitor.

### **9.3. Withdrawal from Study**

Withdrawal from study (including all follow-up) will occur under the following circumstances:

- Withdrawal of consent for follow-up observation by the subject
- Lost to follow-up
- Study completion / termination
- Death

If a subject is lost to follow-up, every reasonable effort should be made by the study site personnel to contact the subject. The measures taken to follow up should be documented.

When a subject withdraws before completing the study, the following information should be documented in the source documents:

- Reason for withdrawal;
- Whether the subject withdraws full consent (ie, withdraws consent to treatment and all further contact) or partial consent (ie, withdraws consent to treatment but agrees to participate in follow-up visits); and/or, withdraws consent from future biomarker research.

## **10. STATISTICAL METHODS AND ANALYSIS**

Statistical analysis will be done by the Sponsor or under the authority of the Sponsor. A general description of the statistical methods to be used to analyze the efficacy and safety data is outlined below. Specific details will be provided in the Statistical Analysis Plan.

### **10.1. Analysis Sets**

#### **10.1.1. Intention-to-Treat Population (ITT)**

The ITT Population is defined as all subjects who are randomized in the study. The ITT population will be used for all efficacy analyses.

The mITT Population is defined as all subjects who are randomized in the study (ITT) and who do not have evidence of progression of underlying malignancy from measurements made at or before the time of randomization. If indicated, the mITT population may be used for additional efficacy analyses.

#### **10.1.2. Safety Population (SP)**

The Safety Population will consist of all randomized subjects who received at least one dose of any study drug.

### **10.2. Sample Size Determination**

The null hypothesis is that the two treatment arms have the same response rate at 48 weeks and the alternative hypothesis is that the response rates of two arms are different.

Assuming a response rate of 30% at 48 weeks for Arm B (placebo + prednisone), a sample size of 186 randomized subjects provides at least 80% power to detect a 20% difference in the response rates at 48 weeks between the 2 treatment arms (Arm A – Arm B) at an alpha level of 5% (2-sided).

No replacement of subjects will be implemented.

### **10.3. Subject Information**

The distribution of subjects by treatment arm for each of the analysis populations will be provided. The number of subjects randomized, dosed, and discontinued will be summarized. Treatment discontinuation will be summarized according to the reasons for discontinuation and by treatment arm.

Demographic and baseline variables and baseline disease characteristics will be summarized by treatment arm.

### **10.4. Efficacy Analyses**

#### **10.4.1. Primary Efficacy Endpoint**

The primary efficacy endpoint of this study is the response rate at 48 weeks (ie, the proportion of responders [CR or PR]). Response will be defined by the NIH Consensus Development Project Criteria (2014).

A subject will not be considered as a responder at 48 weeks if the response was not CR or PR, or if he/she meets any of following criteria:

- Starts a second-line systemic therapy for cGVHD at or prior to the response assessment at 48 weeks
- Has evidence of progression of the underlying malignancy that was the indication for transplant at or prior to response assessment at 48 weeks

Subjects who withdraw from the study prior to, or are missing the response at, 48 weeks will not be considered responders.

The primary efficacy analysis will be performed using the ITT population. The chi-square test will be used to compare the proportions between the two treatment arms.

#### **10.4.2. Secondary Endpoints for Efficacy**

The secondary efficacy endpoints are:

- Response rate at 24 weeks (the proportion of responders [CR or PR]) as defined by the NIH Consensus Development Project (2014)
- Duration of response (DOR) will be defined from the time of initial partial or complete response until progression of cGVHD
- Proportion of subjects with steroid dose reduction to a level of less than 0.15 mg/kg/d at 24 weeks
- Time to withdrawal of all immunosuppressants (with the exception of ibrutinib/placebo)

- Overall survival (OS) is defined as the time from randomization until death due to any cause
- Improvement in Lee cGVHD Symptom Scale scores will be compared between the two treatment arms

Proportion of subjects with improvement in overall score on the Lee cGVHD Symptom Scale and the proportion of subjects with steroid dose reduction will be analyzed using the same method for the primary efficacy endpoint. The Kaplan Meier methodology will be used to estimate the distribution of OS for each treatment group. The log-rank test will be used to compare the OS between the 2 treatment arms. Time to withdrawal of all immunosuppressants will be analyzed using the same method used for OS.

Duration of response is defined as the interval between the date of initial documentation of a response (PR or better), and the date of first documented evidence of progressive cGVHD or death for responders only. Responders will include subjects who achieve response (PR or better) based on NIH 2014 cGVHD criteria. Non-responders will be excluded from the analysis for DOR. Median duration of response will be estimated using Kaplan Meier methodology.

#### **10.4.3. Exploratory Endpoints**

- Pharmacokinetics (PK) parameters of ibrutinib when administered in combination with prednisone in subjects with cGVHD including adolescent subjects
- Pharmacodynamic characteristics (including BTK and ITK occupancy) of ibrutinib in subjects with cGVHD
- Biomarkers relevant to disease biology and therapy with ibrutinib for cGVHD
- Summary scales of SF-36 patient reported outcome

#### **Pharmacokinetic**

Ibrutinib and PCI-45227 bioanalytical data will be used in non-compartmental PK analysis. Plasma concentrations below the lowest quantifiable concentration will be treated as zero in the summary statistics. All subjects and samples excluded from the analysis will be clearly documented in the PK report.

Descriptive statistics will be used to summarize ibrutinib and PCI-45227 concentrations at each sampling time point and PK parameters of ibrutinib and PCI-45227 (including, but not limited to:  $C_{max}$ ,  $t_{max}$ ,  $AUC_{last}$ , and  $t_{1/2}$ ).

Individual and mean plasma ibrutinib and PCI-45227 concentration time profiles will be plotted.

Ibrutinib data from this study may also be combined with data from other studies performed with ibrutinib in subjects with hematologic malignancies as part of a population-PK analysis using nonlinear mixed effects models. For the population-PK analysis, covariates that could potentially

correlate with plasma PK parameters will be evaluated. The results of the population-PK analyses (if performed) will be presented in a separate report.

### **Biomarker and Pharmacodynamics**

The following biomarker assessments will be undertaken:

1. Sequence-directed Immune Function Assessment
2. Cytokine, Chemokine, and Soluble Biomarker Assessment
3. Co-culture Immunologic Function Tests
4. CyTOF-based Phospho-immunophenotyping

PK/PD and biomarkers will be evaluated separately and will not be covered in the statistical analysis plan (SAP).

### **Patient Reported Outcomes**

SF-36 summary scores will be evaluated; detailed analyses will be covered in the statistical analysis plan (SAP).

## **10.5. Safety Analysis**

Analysis of safety data will be conducted on the safety population, which includes randomized subjects who receive at least 1 dose of ibrutinib/placebo. The baseline value is defined as the last value collected on or prior to the first dose date of ibrutinib/placebo, whichever comes first.

The safety variables to be summarized include exposure to ibrutinib/placebo and prednisone, AEs, clinical laboratory test results (hematology and chemistry), Karnofsky/Lansky performance status, and vital sign measurements. In general, safety data will be tabulated or listed. No formal statistical testing is planned.

Growth and development and late effects will be summarized in adolescent subjects.

### **Adverse Events**

The verbatim terms used in the eCRF by investigators to identify AEs will be coded using the Medical Dictionary for Regulatory Activities (MedDRA).

Treatment-emergent period is defined as the period of time from the first dose of study treatment, until the earlier of:

- Thirty days following the last dose of ibrutinib/placebo or prednisone whichever occurs later
- OR

- The start date of a new therapy for cGVHD or for the progression of the underlying malignancy.

The TEAEs are those events that:

- Are not present prior to the treatment-emergent period and occur during the treatment-emergent period,
- Are considered related to study drug by the investigator regardless of the start dates of the events, or
- Are present prior to the treatment-emergent period but worsen in severity during the treatment-emergent period or are subsequently considered related to study drug by the investigator.

All treatment-emergent AEs will be summarized. For each AE, the number and percentage of subjects who experience at least one occurrence of the given event will be summarized. The number and percent of subjects with TEAEs will be summarized according to intensity (CTCAE, v4.03) and drug relationship, as well as categorized by system organ class and preferred term. Summaries and listings may be provided, as appropriate, for those subjects who die, who discontinue treatment due to an AE, or who experience a severe or a SAE.

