### 3. **STUDY DESIGN**

#### 3.1. **Overview of Study Design**

This is a Phase 3, multicenter, international, randomized, double-blind study of oral ibrutinib in combination with prednisone versus placebo in combination with prednisone in subjects with new onset chronic GVHD.

Approximately 186 subjects with newly diagnosed moderate or severe cGVHD, as defined by the 2014 NIH Consensus Development Project Criteria, will be randomized in a 1:1 ratio to receive either ibrutinib in combination with prednisone (Arm A) or placebo in combination with prednisone (Arm B). It is expected that a minimum of 6 subjects in the adolescent group ( $\geq 12$  and  $< 22$  years of age) will be enrolled.

Treatment with ibrutinib/placebo will be administered continuously until unacceptable toxicity, progression of the underlying disease, death, or the start of a new systemic treatment for cGVHD. Progression of the underlying disease will be defined using standard consensus criteria for the individual malignancy.

Corticosteroid therapy will be tapered as per a standard taper regimen with the goal of reducing exposure to high-moderate dose corticosteroids as quickly as possible according to clinical severity of cGVHD. A standard corticosteroid taper schedule is provided in the protocol as guidance to clinicians (Table 4).

The primary endpoint is the response rate at 48 weeks. Response will be defined by the NIH Consensus Development Project Criteria (2014) and must occur:

- In the absence of new therapy for cGVHD
- In the absence of progression of the underlying disease that was the indication for transplant, or PTLD, or death

[figure not shown]
Secondary endpoints will assess for additional clinical benefit including Week-24 response, duration of response (DOR), corticosteroid dose reduction, time to withdrawal of all immunosuppressants, OS, and Lee cGVHD symptom scale. Corticosteroid reduction will be determined by a proportion of patients who are on  $< 0.15$  mg/kg of prednisone at week 24, to allow for variations in corticosteroid taper that occur in practice, while at the same time reaching a dose that minimizes the toxicity associated with steroids.

The randomization between arms will be stratified according to:

- Age group (12 to  $< 22$  years old vs.  $\geq 22$  years old)
- NIH Global Severity grade (moderate vs. severe)
- Ongoing use of systemic immunosuppressants that were initiated for either treatment of or prophylaxis for acute GVHD (Yes vs. No)

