**5.3.1.6. Ibrutinib/Placebo Hold after Withdrawal of All Immunosuppressants**

At the physician's discretion, ibrutinib/placebo may be held if ALL of the following conditions are met:

- All systemic immunosuppressants used for the treatment of cGVHD have been discontinued. (The continued use of very low doses of corticosteroids used only for physiologic adrenal replacement is allowed)
- cGVHD response has been maintained for 12 weeks after complete withdrawal of all immunosuppressants (not including ibrutinib/placebo)
- The subject has received a minimum of 48 weeks of ibrutinib/placebo

If cGVHD returns/worsens after ibrutinib/placebo has been held for the above criteria, ibrutinib/placebo may be re-started after consulting with the medical monitor.

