1.1. Study Design

This is a Phase 3, multicenter, international, randomized, double-blind study of oral ibrutinib in combination with prednisone versus placebo in combination with prednisone in subjects with new onset chronic graft versus host disease (cGVHD).

Approximately 186 subjects with newly diagnosed moderate or severe cGVHD, as defined by the 2014 NIH Consensus Development Project Criteria, were planned to be enrolled. The study enrolled 193 subjects who were randomized in a 1:1 ratio to receive either of the study treatments ibrutinib in combination with prednisone (Arm A) or placebo in combination with prednisone (Arm B).

The randomization between arms was stratified according to:

- Age group (12 to <22 years old vs. ≥ 22 years old)
- NIH Global Severity grade (moderate vs. severe)
- Ongoing use of systemic immunosuppressants that were initiated for either treatment of or prophylaxis for acute GVHD (yes vs. no)

Treatment with the study drug (ibrutinib/placebo) was administered continuously until unacceptable toxicity, progression of the underlying disease, death, or the start of a new systemic treatment for cGVHD. Corticosteroid therapy was tapered as per a standard taper regimen with the goal of reducing exposure to high-moderate dose corticosteroids as quickly as possible according to clinical severity of cGVHD.

Response was assessed according to the NIH Consensus Development Project Criteria (2014).

An independent data monitoring committee (DMC) was established to monitor and review safety and other relevant data on an ongoing basis to ensure the safety of the subjects enrolled in this study and to review results from an interim futility analysis based on data from the first 50 subjects enrolled in the study.

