5. SAFETY

Safety data will be summarized by arm for the safety population and where appropriate for the pediatric subgroup. Table 3 summarizes the planned safety analyses. Adverse events (AEs) will be coded in accordance with the Medical Dictionary for Regulatory Activities (MedDRA) version 22.1. Severity of AEs will be graded by the investigator according to the NCI-CTCAE v4.03 for hematologic and non-hematological AEs.

The primary analysis will use the ibrutinib/placebo treatment-emergent period, which will include all reported AEs satisfying any of the following criteria:

- Those events that occurred or worsened after the first dose of ibrutinib/placebo, through the treatment phase, and within 30 days following the last dose of ibrutinib/placebo or initiation of subsequent cGVHD systemic therapy, whichever occurred first.
- Events with a missing onset date with a resolution date during the ibrutinib/placebo treatment phase; or
- Events that were considered study drug-related regardless of the start date of the event.

For completeness, an additional analysis will be performed to assess AEs that occurred while the patient was being treated with either component of the study treatment (ibrutinib/placebo and/or prednisone; hereinafter referred to as study treatment AEs) and which will include all reported AEs satisfying any of the following criteria:

- Those events that occurred or worsened after the first dose of ibrutinib/placebo or prednisone, through the treatment phase, and within 30 days following the last dose of ibrutinib/placebo or prednisone, or initiation of subsequent cGVHD systemic therapy, whichever occurred first.
- Events with a missing onset date with a resolution date during the ibrutinib/placebo or prednisone treatment phase; or
- Events that were considered related to either ibrutinib/placebo or prednisone regardless of the start date of the event.

Summaries of treatment emergent AEs (TEAEs) and study treatment AEs will be provided, unless otherwise specified.

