All laboratory values will be converted to and reported as international standard (SI) units. In general, only data from the central laboratory will be summarized and analyzed. All gradable laboratory parameters will be graded using the NCI CTCAE v4.03. Unless otherwise specified, only baseline and post-baseline values collected during the ibrutinib/placebo treatment-emergent period will be included in the safety analysis. Additionally, summary of hematologic toxicity will be provided.

Table 3: Summary of Safety Analyses

Assessment Type	Definition	Methods
Study treatment (ibrutinib/placebo and/or prednisone) adverse events	Study treatment AEs, serious study treatment AEs, Grade 3 or higher study treatment AEs, study treatment AEs related to prednisone, study treatment AEs leading to prednisone treatment discontinuation. Study treatment AEs resulted in death Predefined corticosteroid-associated AEs will be summarized	Descriptive summary statistics and/or listings
Ibrutinib/placebo TEAEs	TEAEs, TE SAEs, Grade 3 or worse TEAEs, Related TEAEs TEAEs leading to treatment discontinuation, TEAEs leading to dose reduction. TEAEs related to corticosteroids, TEAEs leading to corticosteroid treatment discontinuation. TEAEs resulting in death Protocol-defined events of special interest (major hemorrhage) and other safety observations Predefined corticosteroid-associated AEs will be summarized	Descriptive summary statistics and/or listings
Central Laboratory results collected during the ibrutinib/placebo TEAE period	Worst post-baseline toxicity grade for selected CTCAE gradable hematology and chemistry laboratory measurements. Liver function abnormalities.	Descriptive summary statistics and/or listings
Vital Signs collected during the ibrutinib/placebo TEAE period	Blood pressure, heart rate	Descriptive summary statistics and/or listings

AE: adverse event; TEAE= treatment-emergent adverse events as defined in Section 5; SAE= serious adverse event; CTCAE= Common Terminology Criteria for Adverse Events.

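### Adverse events are summarised as crude percentages over a window that follows persistence on study drug, so the arms can differ at identical event rates; add cumulative incidence at common times and period-specific rates.

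*Protocol*

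**What the plan says.** - **Measure.** Under Adverse Events in Protocol 10.5, "the number and percentage of subjects who experience at least one occurrence of the given event will be summarized". Steroid-related toxicities in the same section are also given as number and percent. SAP Table 3 gives the method for every safety item as "Descriptive summary statistics and/or listings".
- **Treatment length.** Study drug is "administered continuously until unacceptable toxicity, progression of the underlying disease, death, or the start of a new systemic treatment for cGVHD" (Protocol 3.1; SAP 1.1 agrees). Protocol 9.2 adds "cGVHD progression" as a reason to stop. A hold for sustained response is possible under Protocol 5.3.1.6, but one condition is that "The subject has received a minimum of 48 weeks of ibrutinib/placebo".
- **Window, protocol.** It ends at the earlier of new therapy or "Thirty days following the last dose of ibrutinib/placebo or prednisone whichever occurs later".
- **Window, SAP primary safety analysis.** It follows ibrutinib/placebo only: "within 30 days following the last dose of ibrutinib/placebo or initiation of subsequent cGVHD systemic therapy, whichever occurred first" (Section 5). A second SAP analysis covers ibrutinib/placebo and/or prednisone. Events judged drug-related count whatever their start date.
- **Exposure.** SAP 3.4 tabulates duration and dose by arm. Neither document uses exposure as a denominator for adverse events.
- **Purpose.** Comparing the arms on safety, including steroid-related morbidities, is a secondary objective (Protocol 2.2, SAP 1.2.2). Protocol 10.5 plans no formal safety testing.

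**The concern.** The percentage of subjects with at least one event rises with time at risk. Here time at risk is itself an outcome: it shortens when a subject progresses, stops for toxicity or starts new cGVHD therapy. If persistence differs by arm, the percentages differ even when the drug has no effect on the event rate. Tabulating exposure in a separate table shows the imbalance but does not correct the percentages.

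The steroid-morbidity comparison is the most exposed. A subject who fails and starts new therapy leaves the window, while a subject who does well remains in it and can go on recording hypertension or infection. Longer persistence on ibrutinib could therefore hide a steroid-sparing benefit. Early toxicity stops on ibrutinib would instead make its arm look safer. The SAP's primary window depends more on study-drug persistence than the protocol's, because it ignores continuing prednisone. The second SAP analysis has the same kind of dependence, since it too closes at new therapy.

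**Working it through.** **Inputs from the documents.** Week 48 response is 30% (Arm B), with a 20-point difference, hence 50% (Arm A) (Protocol 10.2). The window has a 30-day tail (SAP 5). 193 subjects were randomised 1:1 (SAP 1.1). The primary analysis comes about one year, and the final analysis about two years, after the last enrolment (SAP 1.5), so earlier enrollees can have more than 48 weeks at risk. The documents give no adverse event rate and no exposure by arm; both are assumed below.

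**The plan's own figure.** Per arm, n = [1.96√(2×0.4×0.6) + 0.8416√(0.3×0.7 + 0.5×0.5)]² / 0.2² = (1.3579 + 0.5708)² / 0.04 = 93, so 186 in total. The plan's sample size reproduces. The point does not depend on it.

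**Model 1: the same constant rate in both arms.** Assume a rate of 0.01 per week. A fraction *s* stays on drug to week *T*; the rest leave uniformly over Weeks 0–48.

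- Risk for a stayer: 1 − exp(−0.01*T*) = 0.617 (*T* = 96) or 0.381 (*T* = 48).
- Risk for a leaver: 1 − (1 − e^−0.48)/0.48 = 0.206.
- False gap = (difference in *s*) × (stayer risk − leaver risk).

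| Assumption | *s*, A v B | Cut | A v B | Gap |
|---|---|---|---|---|
| All non-responders leave | 0.50 v 0.30 | Week 96 | 41.1% v 32.9% | 0.20 × 0.411 = 8.2 points |
| All non-responders leave | 0.50 v 0.30 | Week 48 | 29.4% v 25.8% | 0.20 × 0.175 = 3.5 points |
| Half of non-responders stay | 0.75 v 0.65 | Week 96 | 51.4% v 47.3% | 0.10 × 0.411 = 4.1 points |
| Half of non-responders stay | 0.75 v 0.65 | Week 48 | 33.7% v 32.0% | 0.10 × 0.175 = 1.8 points |

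In the first row, mean exposure is 0.5×96 + 0.5×24 = 60 weeks v 0.3×96 + 0.7×24 = 45.6 weeks. At 0.005 and 0.02 per week that row becomes 24.6% v 19.2% and 60.5% v 50.6%. Adding the 30-day tail (4.3 weeks) to every window multiplies each gap in the table by e^−0.043 = 0.958, so 8.2 becomes 7.9.

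**Model 2: exponential stopping, 30-day tail included.** Rates run from 0.1 to 1.0 per person-year and are equal in both arms.

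| On drug at Week 48, B v A | Cap | Ratio of crude percentages, A/B |
|---|---|---|
| 30% v 50% | 1 year | 1.17 to 1.22 |
| 30% v 50% | 2 years | 1.24 to 1.38 |
| 40% v 50% | 1 or 2 years | 1.07 to 1.17 |
| 50% v 50% | 1 or 2 years | 1.00 |

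First events per person-year gave a ratio of 0.99 to 1.00 throughout, but only because the hazard was constant.

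**Stress test of the remedy.** Prednisone is scheduled to start at 1.0 mg/kg and reach zero at Week 24 (Protocol Table 4), so early clustering of steroid-related events is plausible. Assume 0.03 per week to Week 12 and 0.003 after, the same in both arms, with the exposure of the first Model 1 row.

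- Crude: 37.6% v 34.3%, ratio 1.10.
- Overall first-event rate: 0.376/39.9 = 0.0094 v 0.343/31.2 = 0.0110 per week at risk, ratio 0.85.
- Rates split at Week 24 (expected first events divided by expected weeks at risk in each period): 0.0188 v 0.0193, ratio 0.98; then 0.003 v 0.003, ratio 1.00.

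The single rate is further from 1 than the percentage it would replace. The split rates are close to 1.

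**The case against.** The strongest reply has four parts.

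1. **The protocol is a general description, and descriptive statistics do not exclude rates.** True, but the text commits to none and names only number and percent.
2. **Readers will see exposure by arm and no test is affected.** Also true. This limits the point to a descriptive comparison. A reader might infer an inflated type I error; with no safety testing planned, there is none to inflate.
3. **Response is not persistence.** This stands. Stable disease counts as non-response (Protocol Appendix I) but is not a stopping criterion in Protocol 9.2. A missing Week 48 assessment also counts as non-response (Protocol 10.4.1). Responders may have drug held after 48 weeks. A reader might take 8 points as the expected bias; the documents do not support that, and the gap halves if half of the non-responders stay. With about 96 per arm, the standard error of such a difference is itself about 6 to 7 points.
4. **An exposure-adjusted rate can mislead too.** This stands for a single overall rate, as the stress test shows, and it shapes the remedy.

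Two further inferences should be resisted. One is that ibrutinib will look worse: no exposure by arm is given, and early toxicity stops would reverse the sign. The other is that the window shuts on the day drug stops: the SAP's has a 30-day tail, and the protocol's runs from the later of ibrutinib/placebo or prednisone unless new therapy starts.

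**Conclusion.** The point holds as a moderate one. The only specified measure of adverse events depends on time at risk, time at risk depends on outcome, and comparing the arms on safety is a stated objective. If persistence differs, the comparison is biased in a direction that cannot be known beforehand. Under the assumed rate of 0.01 per week and persistence tied to the design response rates, the false gap is about 2 to 8 points; the upper end needs every non-responder off drug by Week 48 and every responder on it to Week 96. If persistence is equal, there is no bias. Events confined to the first weeks are little affected.

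**What to change.** In SAP Section 5 and Table 3, keep the percentages. For serious and Grade 3 or higher TEAEs, major hemorrhage, infections and the corticosteroid-associated list, add by arm, with 95% CIs:

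- cumulative incidence at Weeks 24 and 48, with death and the start of new cGVHD therapy as competing events and administrative cut-off censored;
- first-event rates per person-year at risk, split into Weeks 0–24 and after Week 24.

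Both are needed. A common horizon removes the part of the gap that builds up later, but competing events still carry differential departure. If every departure in the first Model 1 row were a competing event, 3.5 points would remain at Week 48. At Week 24 it would be 0.20 × (0.213 − 0.162) = 1.0 point, where 0.162 is the leaver risk, the average of 0.111 (left before Week 24) and 0.213 (still on drug then). The split rates address that remainder. The SAP should also state how a window that ends 30 days after the last dose, without death or new therapy, is treated.

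The cost is a few more tables from dates already collected; the SAP already uses cumulative incidence for steroid withdrawal. The downside is that no overall constant-rate figure should be presented alone. Neither addition removes bias from stopping that is related to later risk, because routine collection of adverse events also ends soon after treatment (Protocol 11.4.2).
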